8.2.2.2 EFFICACY ANALYSIS

Primary efficacy assessment:

- Treatment response will be evaluated by calculating the proportion of response of participants who demonstrate a 50% reduction rate or greater at 6 weeks as compared to baseline.

Secondary efficacy assessments:

- Seizure status will be tabulated 14 days following drug initiation; 30 days following drug initiation; 42 days following drug initiation; and 42 days following drug discontinuation. Seizure status will be defined as: **significant response** (at least 50% reduction in seizure frequency as compared to baseline, or no seizures while on medication); **partial response** (25% - 49% reduction in seizure frequency as compared to baseline); **no change**, (0 – 24% reduction in seizure frequency as compared to baseline); and **worsening** (increase in seizure frequency as compared to baseline).

SECTION 9: DATA COLLECTION & MANAGEMENT

Source visit data will be captured via the electronic clinic note during clinic visits. This will then be transcribed on the electronic data collection form which will be developed, maintained and managed via RedCap software. RedCap is a browser-based electronic data capture (EDC) software, in which electronic data collection form (eDCFs) can be custom-built by the user. RedCap is managed and supported by the Clinical Research Unit at the University of Calgary, in collaboration with Cumming School of Medicine. RedCap also maintains an audit trail which tracks a record of initial entries and changes made; time and date of entry; and username of person who made the change.

SECTION 10: ETHICAL ASPECTS

INFORMED CONSENT

The investigator, or designate will obtain signed informed consent/assent from each participant/legal guardian prior to participating in this study as per our departmental SOPs (SOP002: Obtaining Informed Consent V1_2017-08-04; and SOP003: Obtaining Assent, Consent & Decision making Capacity in Minors V1_2017-08-14). Briefly, the investigator or designate will explain the aims, methods, anticipated benefits, and potential hazards of the study. The investigator/designee will also explain that the participant is completely free to refuse to enter the study or to withdraw at any time without any consequence to their future care, for any reason. If new safety information results in significant changes in the risk/benefit assessment, the consent form will be reviewed and updated if necessary. All participants (including those already being treated) will be notified of the new information, and the revised consent form will be given for review for participants to give consent to continue in the study for the revised study.

INSTITUTIONAL REVIEW BOARD

This protocol (and future modifications) along with all other study conduct procedures, and study documentation, will be submitted for review by the Conjoint Health Research Ethics Board (CHREB) at the University of Calgary. The study will not commence until it is approved by the CHREB.

SECTION 11: STUDY DOCUMENTATION, RECORDKEEPING, AND CONFIDENTIALITY OF TRIAL DOCUMENTS AND PARTICIPANT RECORDS

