3.2 RATIONALE FOR STUDY DESIGN

The pre-clinical data for VOR is highly suggestive of a potential novel therapy for the treatment of medically intractable epilepsy. However, VOR is currently approved only for the treatment of cutaneous manifestations in patients with advanced CTCL who have progressive, persistent or recurrent disease subsequent to prior systemic therapies. A safety/efficacy trial of VOR in a population with medically intractable epilepsy is largely warranted, given the existing need for additional therapeutic strategies. The target population will consist of pediatric patients with medically intractable epilepsy, recruited from the Alberta Children's Hospital (ACH) Neurology Outpatient Clinic, with medically intractable epilepsy despite exhaustive treatment with current standard therapies, who would be anticipated to benefit from a novel intervention strategy.

The primary endpoints of this study are the safety & tolerability of VOR in pediatric patients with medically intractable epilepsy. The secondary endpoints of this study is the efficacy of VOR in reducing seizure frequency in this population pool. Participants will receive 230 mg/m²/day of VOR in addition to standard of care anti-seizure medication for a duration of 6 weeks, to evaluate the risk/benefit of VOR at this dosage on top of standard of care anti-seizure treatment.

The proposed study design will allow for the study objectives to be met within the context of a typical Canadian clinical epilepsy treatment centre. Completion of this pilot study in this population will begin to indicate the safety & efficacy profile of VOR at a dosage of 230 mg/m²/day as a potential therapy for the treatment of seizures, and based on findings may justify a larger randomized study to further investigate this potential avenue in children with medically intractable epilepsy in a rapidly translational manner.

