3.3 NUMBER OF SUBJECTS

12 pediatric patients meeting the criteria of medically intractable epilepsy in addition to the other eligibility criteria, recruited from the ACH Neurology Outpatient Clinic will be enrolled in study.

SECTION 4: STUDY POPULATION

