8.1.2 SECONDARY ENDPOINT

The secondary endpoint for this study will be efficacy. Treatment response will be evaluated by:

- Proportion of patients who have at least a 50% reduction in seizures
- Change in seizure remission status

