8.2 STATISTICAL AND ANALYTICAL METHODS

8.2.1 SAMPLE SIZE

The rationale for selection of sample size to investigate safety in a pilot study in this population was based on feasibility in regards to recruitment potential, according to prior knowledge of our referred/existing clinical base, and cost of conducting this study. Further, as this medication has not been tested in this population and rate of AEs in this population is not known, a power based/effect size calculation of sample size cannot be determined.

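### The efficacy analysis is wholly categorical: no point estimate of the size of seizure change, no between-child SD and no interval are planned, although the tracked counts already supply each child's change

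*Combined protocol and SAP*

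**What the plan says.** Efficacy ranks second: "The secondary endpoint for this study will be efficacy" (section 8.1.2). That section lists two measures, the proportion of patients with at least a 50% reduction and a change in remission status. Section 5.2.2.1 names only the first.

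The analysis is in section 8.2.2.2. For the main measure: "Treatment response will be evaluated by calculating the proportion of response of participants who demonstrate a 50% reduction rate or greater at 6 weeks". For the secondary measure: "Seizure status will be tabulated 14 days following drug initiation; 30 days following drug initiation; 42 days following drug initiation", and again 42 days after the drug is stopped. Status has four bands: significant response, partial response ("25% - 49% reduction in seizure frequency as compared to baseline"), no change, and worsening. Any increase, whatever its size, counts as worsening. No summary of percent change, rate ratio, SD, interval or test for seizure frequency is planned.

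Sample size: "12 pediatric patients meeting the criteria of medically intractable epilepsy in addition to the other eligibility criteria" (section 3.3). Section 8.2.1 rests this on feasibility and cost, and says that "a power based/effect size calculation of sample size cannot be determined".

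Seizure data: families track seizures through the 4-week screening period (sections 3.1.2 and 5.1.1). Tracker data since the previous visit are collected at each visit over the 6 treatment weeks (section 5.1.3). Section 2.2 makes seizure reduction the object of the secondary objective. Section 3.2 says the findings "may justify a larger randomized study to further investigate this potential avenue in children with medically intractable epilepsy".

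**The concern.** Every efficacy output is a category. A child with a 49% reduction and a child with none count alike in the responder proportion. The bands separate those two, but put reductions of 25% and 49% together and every degree of worsening together.

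The plan therefore calculates each child's percent change, which the bands require and which the section 7.1.3 rule on a 50% increase also requires, and then reports only the class it falls in. The trial would end without a point estimate of how much seizure frequency changed, without a measure of how much that varied between children, and without an interval. Those are the quantities that the secondary objective is about and that the designers of a follow-on trial would look for first. Section 8.2.1 says no effect-size calculation was possible beforehand, so this pilot is the natural place to obtain them.

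**Working it through.** The plan states no alpha, power, effect size or SD, so there is no planned figure to reproduce. The check has four parts.

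**1. Precision of the responder proportion.** Inputs: 12 children (section 3.3); up to 30% discontinuing for adverse events (section 5.2.1); no replacement (section 4.8). 12 × 0.70 = 8.4, so about 8 may complete. The exact (Clopper-Pearson) 95% limits for x of n are the beta quantiles B(0.025; x, n−x+1) and B(0.975; x+1, n−x).

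| Responders | Proportion | Exact 95% interval |
|---|---|---|
| 4/12 | 33% | 10% to 65% |
| 6/12 | 50% | 21% to 79% |
| 4/8 | 50% | 16% to 84% |

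**2. What a continuous summary would give.** For each child take the log of (seizures per day on treatment ÷ seizures per day at baseline). The 95% interval multiplies and divides the mean ratio by exp(t × SD/√n). At n = 12, t(11) = 2.201. The documents give no SD, so 0.4 to 0.8 is assumed. The example is an observed 30% reduction (ratio 0.70).

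| Assumed SD | Factor | 95% interval, n = 12 |
|---|---|---|
| 0.4 | exp(2.201 × 0.4/3.464) = 1.29 | 10% to 46% reduction |
| 0.6 | 1.46 | 2% increase to 52% reduction |
| 0.8 | 1.66 | 16% increase to 58% reduction |

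With 8 children (t(7) = 2.365) the same SDs give factors of 1.40, 1.65 and 1.95. The intervals become 2% to 50% reduction, 16% increase to 58% reduction, and 37% increase to 64% reduction.

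The SD is itself loosely estimated. With 11 degrees of freedom its 95% limits are SD × √(11/21.92) and SD × √(11/3.816), that is 0.71 and 1.70 times the estimate. An observed 0.6 would run from about 0.43 to 1.02.

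**3. Does the 50% cut cost power?** I compared two one-sided 2.5% analyses of 12 children: an exact binomial test against a known chance response rate, and a one-sample t-test on the log ratio. The assumptions are mine: true rates lognormal with median 7 per week, log-SD 0.8 and floor 3 per week; count variance/mean 2 to 4; period-to-period log-SD 0.2 to 0.35; between-child effect log-SD 0.25; 20,000 trials per setting. For a true 40% reduction, power was about 0.35–0.70 (responder) against 0.52–0.84 (t-test). However, the discrete binomial rule used an actual alpha of only about 0.4% to 1.3%. Randomised to a full 2.5%, the responder test reached about 0.56–0.84, level with the t-test.

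A simpler model, with normal log ratios of constant SD, leaves some gap at equal alpha. At SD 0.6 and a 40% reduction, power is 51% for the exact rule, 58% randomised, and 77% for the t-test. Whether there is a gap therefore depends on assumptions that the documents do not supply.

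**4. Is zero change a clean reference?** Section 4.2 requires at least 3 motor seizures per week, so roughly 12 or more in 4 weeks. When the simulation applies that floor to the observed baseline count with no drug effect, the mean log ratio is about −0.06 to −0.13 rather than 0. The nominal 2.5% t-test against zero then rejects in about 5% to 8% of trials.

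**The case against.** The strongest defence is that this is a safety pilot. Efficacy is secondary, the sample size is openly a matter of feasibility, and section 8.2.2.2 only calculates and tabulates. Nothing the plan promises is broken, section 3.2 says only that the findings may support a larger trial, and the band table gives a coarse distribution of change. All of that stands. It makes this an improvement to a secondary analysis rather than a flaw in the trial's main purpose.

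A second defence is that intervals this wide, with an SD this uncertain, are a weak basis for sizing another trial. That also stands in part, but it favours reporting the interval and the SD so that readers can see how weak the evidence is.

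A reader might infer more than the documents support:

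- **That the 50% cut discards power, as if several children were lost.** The plan has no efficacy test, alpha or power claim. In the count simulation the gap came from the discrete test's unused alpha and closed at equal alpha. In the simpler normal model part of it remained. No loss of a given size is established.
- **That a mean change has a natural no-effect value of zero where a responder rate has none.** With an entry floor and no control arm, regression to the mean shifts both measures.
- **That daily counts are being thrown away.** The documents describe seizure tracking, with an app encouraged, and do not say recording is daily. Totals and days per period are enough.
- **That the plan says nothing about size.** The bands say something, but they give no point estimate and no interval.

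**Conclusion.** The point holds as a low-cost improvement to the efficacy analysis. As written, the plan yields no point estimate of seizure change, no between-child SD and no interval, although the calculation behind each is already required. The imprecision of the responder proportion follows from the planned 12 children, or about 8 at the stated upper discontinuation rate, and needs no further assumption. The widths quoted for the continuous summary rest on assumed log-ratio SDs of 0.4 to 0.8, and a larger SD would widen them.

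The benefit is an effect size, its variability and an interval. It does not make 12 children adequate for an efficacy conclusion, and it does not separate a drug effect from regression to the mean. A claim of lost power should not be attached to it.

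**What to change.** Add to section 8.2.2.2:

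- For each child, the log of (seizures per day on treatment ÷ seizures per day at baseline), adding 0.5 to each count. Use the days actually observed in each period, so that children who stop early contribute, and state which days form each period.
- The mean log ratio with a 95% t-interval, back-transformed to percent change.
- The SD of the log ratio.
- The median percent change with its range.
- A plot showing each child's change.
- The 50% responder proportion, kept as planned, with an exact 95% interval and its denominator.
- A sentence saying that these are descriptive estimates of change from baseline, that regression to the mean remains because there is no control arm and entry requires a minimum seizure frequency, and that zero is not a clean no-effect value.

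The four-band table can stay. The cost is a few lines of text, with no new data, visits or participants. Writing it in before the open-label results are seen also avoids choosing a summary afterwards.

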3.1.2 PHASES OF STUDY

There are three phases to the study.

Phase 1: Screening period

During this phase, participants will be screened for study eligibility, which will last a total of 4 weeks. This will include several baseline investigations including full review of medical history and current medications, seizure frequency, physical examination, vital signs, laboratory safety testing, pregnancy testing for eligible patients, and electrocardiogram (ECG) (see Section 5 Schedule of Assessments and Procedures for complete list of screening procedures). In addition, baseline seizure frequency will be determined during this period. Clinically stable participants, fulfilling all eligibility criteria (see sections 4.2 and 4.3) will be enrolled in the treatment period of the study.

Phase 2: Treatment period

The duration of the treatment period will be 6 weeks. VOR will be given as fixed doses of 230 mg/m²/day. Following the enrollment visit, participants will visit the clinic for 2 more visits every 2 weeks, plus an end of treatment (EOT) visit (see Section 5.1 for detailed schedule). Participants may be seen more frequently for unscheduled visits for follow up of AEs, etc. as per the investigator's discretion. Study visits will include a physical examination, height and weight measurement, vital signs, pregnancy testing (required patients only). Safety monitoring during the treatment period will include laboratory safety testing and ECG. Investigators will review current medications, AEs, seizure diary/frequency at each visit. Investigators will assess study medication adherence at all visits; unused study medication will be returned to site at each visit and new study medication will be dispensed by local pharmacy, as recommended by the investigator. Unused study medication will be destroyed as per local standard operating procedures. All assessments and visit procedures will occur as stipulated in Section 5: Schedule of Assessments and Procedures.

Phase 3: Follow-up period

A safety follow-visit (SFU) will take place 6 weeks after the EOT Visit. The SFU visit will include a physical examination, height and weight measurement, vital signs. Safety monitoring for this visit will include laboratory safety testing and ECG. Investigators will review AEs since last visit and seizure diary/frequency. Any ongoing AEs will be followed by the investigator until resolution or stability.

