4.2 INCLUSION CRITERIA

Patients must meet **ALL** of the following criteria in order to be eligible for this study:

1. Males or females aged 2 – 17 years (inclusive)
2. Medically intractable epilepsy, defined as having failed at least 2 standard anti-seizures therapies and experiencing at least 3 motor seizures per week, separated by at least 24 hours that are quantifiable by observation (e.g. discrete episodes of motor activity). Participants experiencing other seizure types in addition to motor seizures may also be enrolled but must meet the minimal requirement for motor seizures.
3. Ability and willingness of family and/or caregiver (when appropriate) to give written informed consent and to comply with requirement of the study
4. Adequate bone marrow function (defined as an absolute neutrophil count (ANC) of $\geq 2 \times 10^9/L$; platelet count of $\geq 150 \times 10^9/L$; hemoglobin of ≥ 110 g/L [3-11 years], ≥ 120 g/L [females 12 years or over], ≥ 125 g/L [males 12-14 years], ≥ 137 g/L [males 15 years or older])
5. Adequate renal function (defined as serum creatinine $< 1.5X$ age-adjusted upper limit of normal [ULN], or glomerular filtration rate ≥ 70 mL/min/1.73 m²)
6. Adequate hepatic function (defined as total bilirubin < 1.5 times ULN, and alanine aminotransferase [ALT] and aspartate transaminase [AST] < 3 times ULN, and albumin > 33 g/L)
7. Corrected QT (QTc) interval of < 450 msec
8. Prothrombin time (PTT) < 1.5 ULN/International Normalized Ratio (INR) < 1.5 ULN
9. Participants on corticosteroids must be taking a stable or decreasing dose for at least 7 days prior to enrollment

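### The seizure-status table has a one-sided neutral band: a fall of up to 24% is 'no change', but a rise of any size is 'worsening'

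*Combined protocol and SAP*

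**What the plan says.** Section 8.2.2.2 (Efficacy analysis) lists seizure status under the secondary efficacy assessments. It has four categories:

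- 'Worsening' is any "increase in seizure frequency as compared to baseline", without a lower limit on its size.
- The neutral category is confined to a "0 – 24% reduction in seizure frequency as compared to baseline", so it admits no rise at all.
- A fall of 25% to 49% makes a partial response.
- A fall of one half or more, or freedom from seizures on the drug, makes a significant response.

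The timing is stated as "Seizure status will be tabulated 14 days following drug initiation; 30 days following drug initiation; 42 days following drug initiation", with a further tabulation 42 days after the drug is stopped.

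On baseline, Section 3.1.2 (Phases of study) says that "participants will be screened for study eligibility, which will last a total of 4 weeks" and that "baseline seizure frequency will be determined during this period". Inclusion criterion 2 in Section 4.2 requires "experiencing at least 3 motor seizures per week, separated by at least 24 hours". Section 3.3 plans 12 children, in a single open-label arm.

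No section gives a tolerance for small increases in this table. Section 7.1.3 does use a sized increase (50% or more), but for stopping study drug, not for classifying status.

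**The concern.** A child whose underlying rate has not changed will still show a different count in the next period, up about as often as down. The plan absorbs the downward half of that noise, as far as 24%, into 'no change' and sends the whole upward half to 'worsening'. A child going from 20 to 16 seizures over equal periods (−20%) is unchanged; a child going from 20 to 21 (+5%) has worsened.

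This is the only planned display that grades response or shows deterioration in seizures. With 12 children and no control arm, nothing beside the table tells the reader how many 'worse' children an ineffective drug would produce. Section 3.2 says the findings may justify a larger randomized study, so the table may be read with that decision in mind.

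**Working it through.** **No planned figure to reproduce.** The plan states no expected category shares, and Section 8.2.1 sets the sample size on feasibility.

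**Step 1: the bands in counts.** Take a baseline of 20 seizures in 28 days, or 5 per week. The same rate over 42 days gives 20 × 42/28 = 30.

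- 22 seizures: 22/30 − 1 = −26.7%, partial response.
- 23 seizures: 23/30 − 1 = −23.3%, no change.
- 31 seizures: 31/30 − 1 = +3.3%, worsening.

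'No change' therefore runs from 23 to 30, which is seven below the expected count and none above it.

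**Step 2: no drug effect, baseline and follow-up exchangeable.** By approximate symmetry, P('worsening') ≈ (1 − P(exact tie))/2. Ties occur in about 0–7% of children, giving about 0.465 to 0.50. This was checked by simulating 400,000 children per scenario:

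- a 28-day baseline, with follow-up windows of 14, 30 or 42 days;
- assumed rates of 3 to 35 seizures per week;
- Poisson counts, or gamma-Poisson counts with assumed between-period variance of 0.1 or 0.3.

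'Worsening' was 45.5% to 51.1%, or 12 × 0.455 = 5.5 to 12 × 0.511 = 6.1 children.

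**Step 3: entry threshold applied to the baseline count.** Three per week for four weeks is 12 in 28 days. The protocol does not say how the criterion is verified, so using this count is an assumption. Keeping only children with 12 or more selects high baselines, and later counts then tend to fall. Two versions were run.

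- Mixed population (lognormal rates, median 3, 5 or 10 per week, log-SD 0.5 or 1.0, variance 0 to 0.3, windows of 14 and 42 days): 'worsening' was 28.8% to 48.7%, or 12 × 0.288 = 3.5 to 12 × 0.487 = 5.8 children. Rises under 25% alone accounted for 8–36% of all children.
- Fixed true rate of 3 per week: about 22–27% over the same variances and the 14-, 30- and 42-day windows. With Poisson counts at day 42 it is 0.23, and 54% of such children reach the threshold. At 5 per week or more, Poisson counts at day 42 give 0.48–0.50, so selection then matters little.

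**Step 4: a mirrored band, no baseline selection, day 42.** 'Worsening' now needs a rise of 25% or more. In the Step 1 example 30 × 1.25 = 37.5, so 'worsening' starts at 38 and 'no change' runs from 23 to 37.

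| True rate per week | Current rule, Poisson | Mirrored band, Poisson | Mirrored band, variance 0.1–0.3 |
|---|---|---|---|
| 3 | 0.49 | 0.29 | 0.36–0.40 |
| 7 | 0.49 | 0.19 | 0.34–0.40 |
| 14 | 0.50 | 0.11 | 0.33–0.40 |

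Across the 14-, 30- and 42-day windows at these rates, the mirrored band gives about 10–33% with Poisson counts and about 33–40% with the extra variance. In the mixed population with the entry threshold applied, the range falls from 29–49% to 11–35%.

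**Step 5: what 12 children would show.** If the true share is 0.50, P(6 or more of 12 'worse') = 0.61; if it is 0.40, the probability is 0.34. An inert drug could readily produce such a table.

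**The case against.** The strongest reply is that the table carries little weight and errs in a safe direction. It is a descriptive secondary efficacy display, and no test, stopping rule or go/no-go criterion uses the 'worsening' cell. Safety is judged by adverse events, serious adverse events and discontinuations (Sections 5.2.1, 8.1.1 and 8.2.2.1). Worsening of a pre-existing condition is reportable as an adverse event (Section 7.1.1), and marked seizure increases have their own rule in Section 7.1.3. The asymmetry cannot flatter the drug, and the definition is open to anyone who reads it. All of this stands and limits the consequence, but it does not make a one-sided neutral band a sound description of change.

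A reader might infer that half of unaffected children will be labelled worse. The documents do not support that as a general statement: baseline comes from the screening period, so the entry threshold may act on the baseline count and pull the share down. A reader might also treat the table as a planned harm signal, but the plan presents it as efficacy only.

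Two further replies stand. The 25% cut for increases appears nowhere in the plan as a threshold for rises; it is borrowed from the partial-response band. With counts more variable than Poisson, the mirrored band still leaves about a third or more of unaffected children in 'worsening' when there is no baseline selection, so it reduces the problem without removing it. The apparent gaps at 24–25% and 49–50% are whole-percent notation and only editorial.

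**Conclusion.** The point holds as a defect of definition. The asymmetry is plain in Section 8.2.2.2, is not corrected elsewhere, and needs no simulation to establish. Its size does rest on assumed seizure rates and variability: with no drug effect, roughly 30% to 50% of children, about 3.5 to 6 of 12, would be tabulated as 'worsening'. The upper end requires exchangeable baseline and follow-up. Where the entry threshold is applied to the baseline count, the share is lower, and for children with a true rate of 3 per week it is about 22–27%, below that overall range. The counts out of 12 assume every child is classified; the plan does not say how children who stop early are placed in later tabulations. The 50% responder proportion and both response categories are unaffected. This should be corrected, but it is confined to one descriptive table.

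**What to change.** In Section 8.2.2.2, define 'no change' as a change of less than 25% in either direction and 'worsening' as an increase of 25% or more, mirroring the plan's own partial-response cut. List each child's percent change beside the category at every tabulation. As an editorial tidy-up, write the response bands as a reduction of 25% to <50% and of 50% or more, so that they meet.

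The cost is one sentence and one listing. The downside is that rises under 25% lose the 'worsening' label, although they stay visible in the listed changes. If the sponsor prefers to keep the present categories, the listing alone would meet much of the concern. The discontinuation rule in Section 7.1.3 is not touched, and neither the responder endpoint nor the sample size changes.
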